Monthly team videoconferences will be conducted to discuss project progress, recruitment, data collection and analysis, and other issues. The Emory coordinating team will meet weekly. The site co-

investigators and [name] will also meet annually at the ADC Directors' meeting. Additional Data Safety Monitoring Board committee meetings will be held mid-year in years 2 and 3.

Scientific Approach

Design. We aim to enroll 375 subjects in 25 cohorts of 15 subjects each, starting in project month 9 (see project timeline). We expect to enroll, on average, four cohorts per quarter through project year 2 1/2. Recruitment of every 2 cohorts (30 participants total) is scheduled to take place every 6 weeks. We will use a three-arm design with participants randomly assigned on a 2:2:1 ratio to immediate participation in the Tele-Savvy intervention (N=108), immediate participation in an attention control condition (Healthy Living) (N=108), and a usual care condition (N=54). There will be five data-collection points evenly spaced across 12 months. Those in each cohort's intervention condition will take part in Tele-Savvy immediately following baseline data collection. Those in the attention control and usual care conditions will take part in Tele-Savvy after a delay of 6 months (following the 6-month data collection point). Below, we describe the preparation activities in which we will engage (facilitator training and material revisions) and then describe the trial itself. Four NIA-supported Alzheimer's Disease (Research) Centers will collaborate in recruitment, and Emory University will serve as the coordinating center. Emory will be responsible for randomization of subjects (recruits from all sites will be pooled together for randomization), for delivery and fidelity monitoring of the intervention and attention control condition, and for all data gathering and analysis.

Please see the added document for Amendment 8.

Project Timeline, by Quarters

Main Project Activities	Year 1				Year 2				Year 3				Year 4			
	1	2	3	4	1	2	3	4	1	2	3	4	1	2	3	4
Staffing; Training; Finalizing																
DSMB scheduled meetings		X			X				X				X			X
Enroll 18 cohorts (15 each) + Acquisition	30	60	90	120	150	180	210	240	270							
Data Collection																
Data Cleaning and Analysis																
Dissemination																

Preparation.

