meta-analyses. With a final expected sample size of 215 (86, 86, 54 in Tele-Savvy (TS), attention control (AC), and usual care (UC) groups respectively), for the primary intervention test (group-by-time effect) comparing the outcomes of the three group changes from T1 to T2 to T3 (3-by-3 repeated measures design of three groups measured at three time points), at 80% power and 5% significance level, small-to-moderate effect sizes, Cohen's $f = 0.21-0.24$ may be detected for the main effects for group, time and group-by-time interaction effects (given moderate correlation between measurement pairs of $r=0.3-0.5$) (power analysis using PASS 14 Power Analysis and Sample Size Software (2015). NCSS, LLC. Kaysville, Utah, USA, ncss.com/software/pass). After adjusting for any potential group differences, the overall intervention effect of the Tele-Savvy program for the combined T1-to-T3 pre-post effects for the immediate Tele-Savvy group plus the T3-to-T5 pre-post effects from the AC and UC groups will yield a total estimated 215 subjects to perform a pre-post test to detect a small effect size of $d=0.19$ at 80% power and 5% significance level. With the pooled sample, we will be able to also test the mediating effects of mastery and self-efficacy on the Tele-Savvy program for the caregiver outcomes. As shown by Fritz and MacKinnon (2007), sample sizes of 148-196 were adequate to achieve 80% power to detect small-to-moderate effect sizes for the indirect effect of the independent variable on the dependent variable through the mediating variable considering both the Sobel test as well as percentile and bias-corrected bootstrapped approaches.¹⁰⁸ Although our analytic strategy is robust to missing data we will enroll 270 CGs (108 for TS and AC groups and 54 for UC group) per consideration 1 above (maximize accommodation) allowing for an expected 20% attrition. For the exploratory aim comparing the program's efficacy across the 3 ethnicity groups, with an expected final sample size of 215 subjects and proportions of approximately 65% Caucasian, 20% African American, 15% Hispanic, at 80% and 5% level of significance, we will be able to detect moderate effect sizes Cohen's $f=0.19-0.23$ (for 3-group by 2-time point RM-ANOVA for group, time and group-by-time effects).

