Subject Randomization, Coordination, and Retention. Once a cohort of 15 consented subjects has been consented and interviewed, the study statistician ([name]) will use a block randomization scheme to assign equal numbers of members of the cohort to immediate Tele-Savvy or attention control or usual care wait-list participation. As the figure to the right illustrates, the three groups will each, over 12 months, get the Tele-Savvy program. Attention control program will be administered solely to participants who have been randomized to be in attention-control condition initially. Thus, participants who have been randomized to be in Tele-Savvy condition initially or to usual care will not receive attention-control intervention at 6 months post-baseline. Navigators will inform subjects of group assignment and will establish a schedule for participation. For immediate Tele-Savvy participants, start time and time of day for the videoconferences will be set. For those in attention control, start time and time of day for the videoconferences will be set likewise. For those in the usual care condition, an individual schedule of "empathetic calls" will be established. Videoconferences for both Tele-Savvy and attention control will be offered on weekdays (during business hours and evenings) and on weekends to facilitate participation for caregivers who may not be able to join videoconferences on weekdays. Caregivers who might be best served by a Saturday or an evening program will be placed into a block and randomly assigned to Tele-Savvy or attention control conditions. Caregivers for whom weekday participation is non-problematic will be allocated to conditions as described above.

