Aims 1, 2 and 3 (a). Our primary aims are concerned with assessing the effect of the Tele-Savvy program for reducing or retarding the burden, depression, and anxiety of Alzheimer's family caregiving, promoting the quality of life of persons with Alzheimer's (BPSD, agitation; Quality of Life; affect), and enhancing caregiver mastery. We will employ multi-level mixed effects models (MLM) with random (participant) and fixed (cohort) effects to test linear (and non-linear) trajectories of change for the intervention groups and model group X time and group*time interactions. To compare the Tele-Savvy intervention to the attention control and usual care groups, the first 3 time points will be used to test for differences between the 3 group longitudinal trajectories. Additionally, we will combine the intervention effects for the three groups across the main 3 time points from just before receipt of the intervention to immediately after the intervention to the 1st follow-up time point (T1-to-T2-to-T3 for the immediate group and T3-to-T4-to-T5 for the attention control and usual care groups respectively). These combined time points will be referred to as cT1, cT2, cT3. If there are significant differences between or among the 3 groups at the time point immediately prior to receipt of the intervention (cT1), these "baseline" effects will be included and adjusted for in the final model. Overall time effects will be assessed as well as planned post hoc comparisons for immediate effects (cT1 to cT2), longer term effect (cT1 to cT3) and sustained effects (cT2 to cT3). Sidak Type-I error rate adjustment (which has higher power than Bonferroni) will be applied for the multiple pairwise time point comparisons.¹²² Additionally, longer term sustained effects will be captured for the immediate Tele-Savvy group using the additional follow-up times at T4 and T5 for this group. The proposed study design has the advantage of capturing 3 "baseline" time points for the wait-list attention control and usual care groups which will provide an excellent opportunity to evaluate what if any potential "placebo" effects there may be from being enrolled in this type of study.¹²³ These initial

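### The randomisation section contradicts the 2:2:1 ratio and gives evening and weekend caregivers no chance of usual care, so pooled usual-care contrasts are not fully protected by randomisation

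*Combined protocol and SAP*

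**What the plan says.** The Design paragraph of Scientific Approach has "participants randomly assigned on a 2:2:1 ratio to immediate participation in the Tele-Savvy intervention (N=108"), with 108 for attention control and 54 for usual care. Power Analysis and Sample Size Determination repeats those sizes: "we will enroll 270 CGs (108 for TS and AC groups and 54 for UC group").

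Subject Randomization, Coordination, and Retention is the operational instruction. It says that, for each cohort of 15, the statistician will "assign equal numbers of members of the cohort to immediate Tele-Savvy or attention control or usual care wait-list participation". It then makes an exception: caregivers best served by a Saturday or evening program "will be placed into a block and randomly assigned to Tele-Savvy or attention control conditions". The next sentence reads "Caregivers for whom weekday participation is non-problematic will be allocated to conditions as described above". No ratio is given for the two-arm block.

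Under Aims 1, 2 and 3 (a), "the first 3 time points will be used to test for differences between the 3 group longitudinal trajectories". The model has a random participant effect and a fixed cohort effect. Schedule is not named as a stratum or covariate, and no text limits usual-care contrasts to caregivers who could have been assigned to usual care.

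The Design paragraph also says "We aim to enroll 375 subjects in 25 cohorts of 15 subjects each" and refers to a separate Amendment 8 document, which was not available for this check.

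**The concern.** There are two problems, and only the second affects validity.

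1. **Two allocation rules.** An even three-way split and 2:2:1 produce different lists. The choice changes which comparison is favoured.

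2. **A stratum without usual care.** Needing an evening or Saturday slot is known before randomisation, and it sets the chance of usual care to zero. Tele-Savvy and attention control will contain such caregivers and usual care will not. Schedule need may go with employment, co-residence or intensity of care, and so with change in burden, depression or anxiety. The exposed results are the pooled Tele-Savvy versus usual-care and attention-control versus usual-care contrasts and the three-group test. Comparisons among weekday caregivers are not exposed. Nor is Tele-Savvy versus attention control, provided the evening/weekend block is split 1:1 like the weekday cohorts.

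**Working it through.** **Allocation arithmetic.** In a cohort of 15, 2:2:1 gives 6/6/3. Over 18 cohorts that is 108/108/54, the plan's own figure. An even split gives 5/5/5, or 90/90/90, which matches none of the stated arm sizes. The Tele-Savvy description gives an average group of six, which fits 6/6/3.

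**Inputs for the second problem.** N = 270 and 20% attrition come from the power section. The following are assumptions, because the documents give no figures:
- evening/weekend share *e* of enrolment: 5%, 10% or 20%;
- 1:1 split within that block;
- difference δ in six-month change between evening/weekend and weekday caregivers: 0.3 or 0.5 SD of change.

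**Formulas, weekday 2:2:1.**
- Tele-Savvy enrolled = 270 × [0.4(1 − e) + 0.5e]
- Usual care enrolled = 270 × 0.2(1 − e)
- Evening/weekend share of Tele-Savvy, s = 0.5e / [0.4(1 − e) + 0.5e]; share of usual care = 0
- Bias in pooled Tele-Savvy versus usual care = s × δ
- Type I error: two-sample t test with noncentrality sδ / √(1/n₁ + 1/n₂), where n₁ and n₂ are 80% of enrolment

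For e = 20%, Tele-Savvy = 270 × (0.32 + 0.10) = 113.4, usual care = 270 × 0.16 = 43.2, and s = 0.10/0.42 = 23.8%. With δ = 0.3 the bias is 0.238 × 0.3 = 0.071 SD. After attrition the groups are 90.7 and 34.6, so √(1/90.7 + 1/34.6) = 0.200. The noncentrality is 0.071/0.200 = 0.36, and the two-sided error is 6.4%.

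| Weekday rule | e | δ (SD) | Tele-Savvy / usual care enrolled | s | Bias (SD) | Type I error |
|---|---|---|---|---|---|---|
| 2:2:1 | 5% | 0.3 | 109 / 51 | 6.2% | 0.02 | 5.1% |
| 2:2:1 | 10% | 0.3 | 111 / 49 | 12.2% | 0.04 | 5.4% |
| 2:2:1 | 20% | 0.3 | 113 / 43 | 23.8% | 0.07 | 6.4% |
| 2:2:1 | 20% | 0.5 | 113 / 43 | 23.8% | 0.12 | about 9% |
| Even split | 10% | 0.3 | 95 / 81 | 14.3% | 0.04 | 5.7% |
| Even split | 20% | 0.3 | 99 / 72 | 27.3% | 0.08 | 7.5% |
| Even split | 20% | 0.5 | 99 / 72 | 27.3% | 0.14 | about 12% |

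**Planned group-by-time test.** This was simulated with three groups, three times, within-person correlation 0.5 and a stratum difference that grows linearly. At a 20% share, type I error under weekday 2:2:1 is about 5.6–5.8% (δ = 0.3) and 6.4–6.8% (δ = 0.5). Under an even weekday split it is about 6.2–6.4% and 8.5–8.8%. With stratum and stratum-by-time terms added it returns to about 5% in every scenario, and the bias to 0.00.

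**Effect of the ratio on precision.** Detectable standardised difference at 80% power, two-sided 5%, N = 270 with 20% attrition:
- Tele-Savvy versus attention control: 0.43 under 2:2:1 (86 v 86); 0.47 under an even split (72 v 72).
- Tele-Savvy versus usual care: 0.53 under 2:2:1 (86 v 43); 0.47 under an even split (72 v 72).

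Usual care is taken as 43 because 86 + 86 + 43 = 215, the stated final total. The printed 86, 86 and 54 sum to 226. With 54, the 0.53 becomes 0.49.

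**The case against.** **Intent is fairly clear.** The ratio, the arm sizes and the group size of six all point to 2:2:1, so the even split may be a drafting slip. That is largely right, and the planned f of 0.21–0.24, which depends on total N, does not move. The randomisation section is still the instruction from which the list is made. The two rules would agree on 108/108/54 if exactly 40% of enrolment were in evening/weekend blocks (weekday 162/3 = 54 per arm, plus 54 each to Tele-Savvy and attention control). But Limitations and Challenges describes such programs as occasional, and Design states 2:2:1 outright.

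**Some governing text is unseen.** Amendment 8 and the figure beside the randomisation section might address allocation. Neither was available. That is a reason to reconcile against them; it does not repair the conflicting text.

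**The larger biases are speculative.** This stands. Share and difference are both assumed. A 0.5 SD gap in change by schedule need would be within the range of the pilot's own pre-post effects (0.40 to 0.55), and nothing in the plan suggests it. The 12% figure also needs a literal even split.

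**The plan already adjusts.** The Analytic approach paragraph examines predisposing factors against baseline and change, and controls those with significant baseline associations. Predictors of missingness are added as well. This may capture part of the difference, but schedule is not named and adjustment depends on a significance test. The fixed cohort effect shifts level, whereas the group-by-time test concerns change.

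**Conclusion.** The concern holds. The conflict between allocation rules is certain on the text. So is the zero chance of usual care for evening and Saturday caregivers, read together with the sentence that sends the others through the three-arm scheme. The right conclusion is that pooled usual-care contrasts are not fully protected by randomisation; it has not been shown that they are biased. If the evening/weekend share is about 5–10%, the consequence is negligible: at most 0.04 SD and 5.4% at an assumed 0.3 SD difference with weekday 2:2:1. It becomes material at a share near 20%: 0.07–0.12 SD, and 6.4% to about 9% for the pairwise test. If the two strata change alike, there is no bias. This should be fixed because the exposure is avoidable and the remedy is cheap.

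**What to change.** **Protocol text.** State one rule: every block, including evening and weekend blocks, is randomised 2:2:1 over all three arms (6/6/3 per 15). Replace the even-split wording, put the enrolment total (270 or 375) beside the rule, and check both against Amendment 8. Group scheduling is no obstacle before month 6: "For those in the usual care condition, an individual schedule of" calls is all that the plan sets up, with no group videoconference slot.

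**Caregivers already randomised under the two-arm rule.** Record the schedule stratum, add stratum and stratum-by-time to the model, and estimate usual-care contrasts within the weekday stratum. If allocation is already complete, this is the only part that can still be acted on. State also the ratio used inside the two-arm blocks, since the Tele-Savvy versus attention-control comparison relies on its matching the weekday ratio.

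**Cost.** One or two sentences and a new allocation list. With groups of six, an evening/weekend block needs 15 caregivers instead of 12 to fill one Tele-Savvy and one attention-control group, so it may fill more slowly. Restricting usual-care contrasts to weekday caregivers costs some precision. At N = 270 with weekday 2:2:1, the detectable Tele-Savvy versus usual-care difference rises from 0.53 to about 0.55 at a 10% share (78 v 39) and 0.59 at 20% (69 v 35). Those contrasts then describe weekday caregivers only.

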Subjects. Participants will be informal caregivers (family/friends) of persons living with Alzheimer’s disease or another dementia. Participants must be providing at least 4 hours per day unpaid assistance, on average, for a person in the early-middle stage of illness (Clinical Dementia Rating of ≥ 1 by home ADC) who is community-dwelling and for whom there is no established plan for institutionalization in the next six months. Caregiver may or may not reside with their care recipient, but care recipients must live in the community and not in an assisted living facility, nursing home, or another institutional setting. The participant must not be involved in another caregiver training study and must not have participated in in-person Savvy Caregiver Program or Tele-Savvy previously. Each participant must have access to a computer or a mobile device with adequate internet connection, microphone, and speakers (to be able to participate in teleconferences) and be able to use email (this was not a serious barrier in the pilot studies). Participants must be able to read, speak and understand English and have no uncorrectable vision or hearing deficits that might impede participation. Questions posed after explaining the project during eligibility determination and the consent process will be used to gauge caregivers’ cognitive ability to take part in the project. Webcams will be mailed to those caregivers who do not have them for the duration of the entire program and caregivers will be asked to mail webcams back after participation in Tele-Savvy.

Power Analysis and Sample Size Determination Several considerations enter into sample size determination: (1) our wish to accommodate as many caregivers as feasible given time/resources; (2) our experience and prior results from SCP trials; (3) sample and effect sizes/attrition rates in recent dementia CG

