After navigators inform caregivers about their condition assignment and establish a schedule for participation for those in immediate Tele-Savvy and attention control groups, navigators will conduct individual videoconferences to introduce them to Canvas, a widely used course management platform that will house the daily video lessons. Canvas allows participants to view video lessons at their own convenience and as often as they wish, but it does not allow them to disseminate them. It allows us to track individual use, so we can monitor the "dose" of each participant's viewing. Navigators will teach caregivers how to login and access materials in Canvas and will provide navigators' contact information, reinforcing that caregivers should contact navigators for technical assistance at any time. Canvas also allows us to post evaluation questionnaires. The videoconference will provide participants with another opportunity to practice with Vidyo and to practice opening the lessons (during their participation in Tele-Savvy, navigators will send emails to remind them to access the lessons). The procedure for orienting participants to Canvas will be provided to usual care group participants following the 6-month data collection point and prior to their entry to the Tele-Savvy program. In an effort to keep them engaged in the study, regardless of group assignment, all subjects will receive a monthly study newsletter that will provide information about practices to promote healthy living drawn from NIA's Go4Life program. The e-newsletters will be sent by local site coordinators.

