Wait List Attention Control Group Condition and Participation. The attention control condition consists of video and text materials on exercise, diet, and healthy living drawn from the NIA Go4Life program. While these materials provide important and beneficial information, we believe they will not affect our postulated key mediators (mood, mastery and care recipient quality of life). They will provide equal attention, but should not confound the trial. The same number of brief modules as employed in Tele-Savvy (36) will be provided over the course of six weeks; videos will emerge on Canvas site weekly in a manner similar to the Tele-Savvy condition described above. Likewise, navigator will send attention control participants weekly reminder e-mails to log into Canvas and view daily videos. All attention-control participants will convene weekly for a videoconference that will mirror Tele-Savvy videoconference in format and length but will differ in content. Specifically, attention control videoconferences will not contain any information on caregiving strategies, but rather will center on the application of healthy living strategies. A standard structure of each videoconference will be employed by attention-control facilitators: (1) Facilitators greet and check in with each of the caregivers; (2) coaching and debriefing (e.g., hearing how (after the first week) caregivers did with the homework, answering questions and/or responding to feedback about the week's material; (3) review of key points and concepts from the week's video sessions and introduction of new material; (4) reports on any activities that caregivers may have implemented based on the Go4Life materials; (5) provision of homework assignments and adjournment.

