Usual Care. Those randomized to this group will be encouraged to continue to receive care for the person living with dementia through whatever arrangement had been in place. Since this group will represent a sort of natural history of caregiving, we will not, with one exception, ask them to restrict any activity they might undertake to seek care for the person or information for themselves. The exception we will request is that, during the 6-month period, they not enroll in an extended caregiver education program. If, in the course of these 6 months, they participate in support groups, visit education web sites, attend informational seminars and/or consult with their health care providers, that will be fine. These are all part of the natural history.

Approximately four months after initial data collection, attention-control and usual care participants will be contacted to schedule their participation in Tele-Savvy which will begin 6 months after their baseline assessment. Their Tele-Savvy experience will be exactly the same as that described above (**Immediate Participation Group Procedures**). These participants will be offered the opportunity of another practice session with Vidyo and Canvas prior to the beginning of Tele-Savvy.

Category	Instrument	Instrument Description	Psychometrics
Baseline Only PLWA Cognitive Status	Informant Questionnaire on Cognitive Decline in the Elderly (IQCODE),	A 16-item rating scale (can be informant completed) not contaminated by education	Correlates well with dementia diagnosis; predicts dementia dx as well or better than the MMSE. ¹⁰⁹⁻¹¹⁰
Demographic Information	Demographic sheet Caregiving History	SES, PLWA information, length of caregiving, co-residence with recipient.	Study-developed form (Baseline only)
PLWA ADLs	Lawton ADL/IADL scale	13-item scale elicits caregiver assessment of PLWA ADL and IADL functioning	Interrater reliability between .87-.91 ¹¹¹
[Caregiver Vars] Appraisal: Stress	Perceived Stress Scale	14-item Likert-type questionnaire; higher scores reflect higher perceived stress	Internal consistency ranges reported at 0.84 or higher. ¹¹²

Depression	Center for Epidemiological Studies-Depression	A 20 item Likert scale scored 0-3 with somatic and psychological subscales	Alpha=.85 for general population; validity well-established ⁹⁸
Anxiety	State-Trait Anxiety Inventory	A 20-item 4-point Likert scale is sensitive to changes in transitory anxiety	STAI state sensitive reliability reported at .94 ⁹⁹

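### Only usual care is asked to stay out of extended caregiver education during the controlled six months, and no arm's use of outside programs is recorded

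*Combined protocol and SAP*

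**What the plan says.** The Usual Care section of the combined protocol and SAP sets out the arm's role: "Since this group will represent a sort of natural history of caregiving, we will not, with one exception, ask them to restrict any activity". The exception follows: "The exception we will request is that, during the 6-month period, they not enroll in an extended caregiver education program". Support groups, educational web sites, informational seminars and provider consultations remain open to these caregivers.

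The sections Immediate Participation Group Procedures and Wait List Attention Control Group Condition and Participation contain no such request. The Subjects section applies to everyone: "The participant must not be involved in another caregiver training study". It also excludes earlier participation in in-person Savvy or in Tele-Savvy.

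Two other features bear on how usual care is described, both in Subject Randomization, Coordination, and Retention. The first begins "For those in the usual care condition, an individual schedule of" and goes on to name empathetic calls, which are not defined there or elsewhere in the text available. The second is that "all subjects will receive a monthly study newsletter that will provide information about practices to promote healthy living drawn from NIA's Go4Life program".

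Under Aims 1, 2 and 3 (a), the three arms are compared over the first three time points (baseline, months 3 and 6). Month 6 is then reused as the pre-intervention value, cT1, for the two wait-list arms.

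**The concern.** A caregiver in attention control or immediate Tele-Savvy could join an ordinary community caregiver course after randomization without going against anything in the visible text, while a usual care caregiver has been asked not to. The protocol gives reason to take this seriously. Savvy Caregiver runs in more than a dozen states, recruitment goes through community agencies and Alzheimer's Association chapters, and earlier exposure to Savvy excludes a candidate at entry.

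Two analyses are exposed. In the baseline-to-month-6 comparison, outside courses would be a co-intervention whose frequency may depend on the arm. In the pooled pre-post analysis, a course taken before month 6 would already have moved a wait-list caregiver's cT1 value. The plan adjusts for cT1 if the groups differ significantly there. That deals with differences in level, not with the exposure itself, which nobody records.

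**Working it through.** **Step 1: the arms side by side, baseline to month 6.** No sample-size or power figure is involved, so there is no plan figure to reproduce.

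| Feature | Tele-Savvy | Attention control | Usual care |
|---|---|---|---|
| Entry rule on training studies and earlier Savvy or Tele-Savvy | yes | yes | yes |
| Request to avoid extended caregiver education | not stated | not stated | yes |
| Study contact | weekly group videoconferences, video modules | the same format, other content | empathetic calls (number, length, content, caller not stated) |
| Monthly Go4Life newsletter | yes | yes | yes |
| Outside programs recorded | not stated | not stated | not stated |

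The second row is the asymmetry. For the last row, I looked through the instrument table, Data Collection, and Variables and Measures. They cover standardized scales, a baseline demographic and caregiving-history form, viewing of the study's own videos, videoconference attendance, self-reported caregiving behaviors, program evaluations and technical problems. None is an item on outside programs.

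**Step 2: what uneven uptake could do.** The following inputs are assumptions, because the documents give none:

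- E is the Tele-Savvy effect with no outside programs, and both control conditions are inert.
- An outside course taken alone is worth E.
- A share *p* takes one in each arm that received no request, and nobody does in usual care.
- A fraction *a* of the course's benefit adds to Tele-Savvy for those who have both.

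Arm means, as shifts from no exposure, are E + *ap*E (Tele-Savvy), *p*E (attention control) and 0 (usual care). Hence:

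- Tele-Savvy minus attention control = E[1 − *p*(1 − *a*)]
- Tele-Savvy minus usual care = E(1 + *ap*)
- Attention control minus usual care = *p*E

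As multiples of E:

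| *p* | *a* | vs attention control | vs usual care | between controls |
|---|---|---|---|---|
| 0.05 | 0 | 0.95 | 1.00 | 0.05 |
| 0.05 | 1 | 1.00 | 1.05 | 0.05 |
| 0.10 | 0 | 0.90 | 1.00 | 0.10 |
| 0.10 | 1 | 1.00 | 1.10 | 0.10 |
| 0.20 | 0 | 0.80 | 1.00 | 0.20 |
| 0.20 | 1 | 1.00 | 1.20 | 0.20 |

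**Step 3: reading it.** Full dilution against attention control (*a* = 0) and full inflation against usual care (*a* = 1) are opposite extremes and cannot both occur. At *a* = 0.5 and *p* = 0.10, each is half as large: 1 − 0.10 × 0.5 = 0.95 and 1 + 0.10 × 0.5 = 1.05. The gap between the two controls, *p*E, does not depend on *a*. If usual care caregivers ignore the request and take courses at the same rate *p*, that gap becomes *p*E − *p*E = 0. The calls could also move the usual care mean, by an amount that nothing in the documents allows one to estimate.

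**The case against.** The case against making much of this is strong in several respects.

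- **Uptake may be low.** The trial's rationale is that travel, time and the need for substitute care keep many caregivers out of in-person courses. Attention control caregivers also know that Tele-Savvy is coming at month 6. This stands: a high *p* is unsupported.
- **Usual care is asked, not barred.** The request covers extended programs only. This stands; the difference in behavior may be smaller than the difference in wording.
- **Part of the file is not visible.** Consent pages were removed and the Design section points to a separate Amendment 8 document. Participant instructions may be there, so the finding is limited to the text available.
- **Outside programs may be part of the Tele-Savvy effect.** The curriculum includes all elements of Savvy, whose topics include community resources. Restricting that arm could suppress something it teaches. This stands, and the fix allows for it.

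A reader might also infer that usual care is mislabeled or that the newsletter contaminates it. The documents do not support that. The wording is hedged ("Since this group will represent a sort of natural history of caregiving") and the education request is disclosed. The newsletter goes to every arm for retention, so it is not unequal handling. It does share a source with the comparator: "The attention control condition consists of video and text materials on exercise, diet, and healthy living drawn from the NIA Go4Life program". But the protocol expects even that full condition not to affect its key mediators, and nothing shows that about six monthly issues would. Contact differs between arms by design; what can fairly be said of the calls is that they are undefined and missing from the Usual Care section.

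What none of this answers is that a stated rule is applied to one of two wait-list controls and that outside exposure is not measured in any arm.

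**Conclusion.** The point holds in a limited form. On the visible text, the request to avoid extended caregiver education is made to usual care alone, and outside program use is not captured. Differential co-intervention before month 6 is therefore possible, could affect both the three-group comparison and the wait-list arms' cT1 value, and could not be detected or examined afterwards.

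Its size and net direction cannot be derived. The multiples in the working illustrate assumed uptake of 5% to 20% and an outside course as effective as Tele-Savvy; they are not estimates. It would be wrong to conclude that the Tele-Savvy effect is biased in a known direction or that the comparators are compromised. This is a cheap improvement that should be made.

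**What to change.** 1. In Wait List Attention Control Group Condition and Participation, make the same request as in Usual Care, through the month-6 interview.
2. In Immediate Participation Group Procedures, either make the same request or state why not, given that community resources are part of the curriculum.
3. Add one item to every interview, in all arms, on extended caregiver programs attended since the last interview. Prespecify a sensitivity analysis by that exposure for the three-group comparison and the cT1-based analysis. Exposure arises after randomization, so this should support the primary comparison as randomized, not replace it.
4. In Usual Care, describe the arm as usual care plus the empathetic calls and the all-arm newsletter, and state the calls' number, length, content and caller. The newsletter itself need not change.

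The cost is a few sentences and one question per interview. The request remains voluntary. If enrollment is under way, the change can reach later cohorts only; cohorts will then have been handled differently, and the earlier asymmetry and unrecorded exposure should be reported as a limitation.
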